After an initial phone screening to determine eligibility, interested families will be invited to attend an orientation at the Healthy Eating and Activity Laboratory (HEAL) at the University of Tennessee Knoxville. For families who agree to participate, caregivers will complete informed consent forms and children will provide assent. After consent/assent, families will complete baseline assessment measures (see Measures). Immediately after baseline measures are completed, families will be told their assigned condition (randomized using a random numbers table). All families will be provided information on the benefits of DSM and the relationships of the four targeted food groups with child health. Families will be informed that the child's DSM records over the next 4 weeks will be used to provide individualized feedback on their child's nutrition status at their follow-up visit, at which time they will receive access to a short online behavioral nutrition education program (described below).

Each family will be provided a access to a dDSM log that matches group assignment. Caregivers will be instructed to review their child's DSM each day and complete a caregiver check in. Additionally, to get children started, all caregivers will be instructed to sit with their child each day for the first 3 days of the DSM period to help their child log any foods consumed

from targeted food groups. If no logging is completed within the first 4 days of a family's DSM period, a research assistant will reach out to the caregiver to problem solve and provide support.

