At the end of the 4-week DSM period, families will schedule a virtual appointment to complete follow-up assessment measures. To provide feedback to families, days for which tracking was marked as completed in the dDSM log will be entered into the Nutrition Data System for Research (NDSR) software to determine servings of fruits and vegetables consumed, as well as intake of added sugars and saturated fats from sugar-sweetened beverages and sweet and salty snack foods. These values will be entered into a feedback template that compares the child's intake to the recommendations in the Dietary Guidelines for Americans (DGA) 2020-2025. Families will also be provided access to a short online behavioral nutrition education program that will consist of four modules: 1) DGA recommendations and basic nutrition information, 2) establishing a healthy home environment, 3) positive reinforcement of healthy behaviors, and 4) pre-planning and problem solving.

Family dDSM Training. After baseline measures, families will complete a DSM practice session using their dDSM log under the observation of research staff. The family's personal dDSM will be used; therefore, GAME/PRAISE features related to the family's assigned condition will be included. The family will practice logging foods and beverages from a standard list and will then be instructed to mark logging as complete for the day. Research staff will answer any questions the family has and will explain how to use the "Help Me Log" feature. Caregivers will also be shown how to complete the caregiver check in feature.

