For families randomized to the PRAISE conditions (PRAISE and PRAISE+GAME), caregivers will also provide praise to their child during the DSM practice session so that research staff can observe and provide feedback. During training session, caregivers will be provided a brief training on providing process praise. A description of process praise will be provided, including a list of examples, and caregivers will complete a brief "quiz" in which they attempt to correctly identify process praise statements. Caregivers will also be encouraged to avoid negative reinforcement (e.g., nagging). If the caregiver notices the child is not using the dDSM log, he or she will be encouraged to engage in problem solving/preplanning (rather than nagging) to encourage the child to self-monitor. If the caregiver notices the child is engaging in undesirable behaviors (e.g., recording unhealthy foods), this should be ignored rather than criticized. Additionally, caregivers will be encouraged to provide the praise as close to the occurrence of the behavior as possible to increase its effectiveness. For PRAISE conditions, completion of the caregiver check-in will prompt the caregiver to also complete a praise check-in ("Would you also like to complete a praise check in?"). If no praise check-ins are completed within the first 4 days of the DSM period, a research assistant will reach out to the caregiver to problem solve and provide support.

For families randomized to GAME conditions (GAME and PRAISE+GAME), children and caregivers will observe how points are accrued during the DSM practice session. Prior to the practice session, research staff will explain how points are earned and how points help to "level up" the virtual pet. Points will be accrued and represented in the dDSM log in real time so that children will immediately be rewarded for engaging in DSM behaviors.

At the conclusion of the study, results will be disseminated to former participants via email.

Sample Size

Targeted enrollment will be 40 families (10 families per group) for the proof-of-concept trial.

Measures

Sample characteristics

Demographics. Demographic information will be used to describe the study sample. Information collected will include child and caregiver age, race and ethnicity, and gender and caregiver marital status, education level, employment status, and household income.

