Child height and weight. Child height and weight will be collected to confirm study eligibility, and BMI z-score will be calculated based on sex and age.

Parenting style. Previous research has associated parenting style with intrinsic motivation in children. To determine parenting style, caregivers will complete Parenting Styles and Dimensions Questionnaire (PSDQ)-Short Version. The PDSQ-Short Version is a 32-item questionnaire that uses a 5-point Likert scale (never to always) to provide scores for three parenting style factors: authoritativeness, authoritarianism, and permissiveness.

Primary measures: DSM behaviors

Foods, beverages, and serving sizes entered in the dDSM logs by participants will automatically populate a web-based spreadsheet that will collect participant ID number, date and time of entry, food/beverage name, and serving size. This spreadsheet will be exported to Microsoft Excel, and data management and analysis will be conducted in SAS Enterprise Guide 8.3.

Frequency. I.e., number of days with any logging. DSM frequency has been shown to predict success in family-based based childhood overweight and obesity programs. A day will be counted as “tracked” if any food or beverage is logged on that day or, if no food or beverage is logged, the “Logging Complete” button is clicked.

Timing. I.e., proportion of days on which food/beverage items were tracked on the day of intake, as well as the average number of logging sessions per day. Sessions will be considered as distinct tracking events if they occur >15 minutes apart.

Secondary measures

Child intrinsic motivation. Gamification and caregiver praise may differentially affect child motivation to engage in DSM. The Task Evaluation Questionnaire of the Intrinsic Motivation Inventory (IMI) will be used to determine whether are differences in pre-post changes in child intrinsic motivation. This questionnaire consists of 22 items and utilizes a 5-point Likert scale (not at all true to very true) to assess interest/enjoyment, perceived choice, perceived competence, and pressure/tension. At baseline, the measure will be administered after the child has practiced using dDSM with the research assistant so that he or she has some familiarity with the behavior before completing the measure.

Child motivation to change eating behaviors. Child’s motivation to change eating habits will be measured, as this may influence engagement in DSM. Children will be asked to complete the

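### The protocol gives conflicting orders for the baseline IMI and the practice session, so the score used as baseline may be taken after exposure to praise or gamification

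*Combined protocol and SAP*

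**What the plan says.** Three places in the combined protocol and SAP fix the order of the first visit.

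- **Study Flow.** Baseline measures follow consent and assent, with a pointer to the Measures section, where the IMI is listed. Then: "Immediately after baseline measures are completed, families will be told their assigned condition".
- **Family dDSM Training.** "After baseline measures, families will complete a DSM practice session using their dDSM log under the observation of research staff". On the log used: "The family's personal dDSM will be used; therefore, GAME/PRAISE features related to the family's assigned condition will be included". In the game conditions, "children and caregivers will observe how points are accrued during the DSM practice session", and points appear in real time so that "children will immediately be rewarded for engaging in DSM behaviors". In the praise conditions, "caregivers will also provide praise to their child during the DSM practice session".
- **Measures, Child intrinsic motivation.** "At baseline, the measure will be administered after the child has practiced using dDSM with the research assistant". The stated reason is that the child should know the task before rating it. The entry gives the purpose of the IMI as detecting differences in pre-post change, on the ground that "Gamification and caregiver praise may differentially affect child motivation to engage in DSM".

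Statistical Analysis uses the baseline IMI twice: as the covariate in the 2x2 ANCOVA of follow-up IMI, and as the first level of time in the mixed ANOVA.

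**The concern.** Under the first two places the IMI, as a baseline measure, comes before practice. Under the third it comes after. Nothing exempts the IMI from the general order, so with a single practice session staff cannot follow all three.

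If staff follow the IMI entry and use the session that is described, the child has by then learned the condition and received a first dose of it. The first score is then partly an outcome. Adjusting for it, or subtracting it, removes some of the effect when practice and the four weeks push motivation the same way, and adds to the effect when they push in opposite directions.

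Either direction is plausible. Immediate points could raise interest, but the IMI also scores pressure/tension and perceived choice, and the protocol itself expects the two strategies to act differently.

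At stake are the IMI analyses only. The primary outcomes, self-monitoring frequency and timing, are analysed without a baseline covariate. No other baseline questionnaire is tied to practice.

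**Working it through.** The plan states no figure to reproduce here. The check sets the passages side by side and then works out the consequence for the planned analyses.

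**Order of events**

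| Source | Order stated or implied |
|---|---|
| Study Flow | consent, baseline measures, disclosure |
| Family dDSM Training | baseline measures, then practice with assigned features |
| Child intrinsic motivation | practice, then baseline IMI |

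The first two rows agree with each other. The third agrees with them only if there is another practice, before disclosure and without features. No section describes one.

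**Inputs.** From Sample Size: 40 families, 10 per cell, so 20 against 20 for each main effect. Everything else is an assumption because the documents give no value: IMI in SD units, SD 1 at both visits, correlation rho, shift e at the first IMI and effect T at follow-up (both in the game arms), two-sided 5% level.

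**What each analysis estimates.** With equal SDs the within-cell slope is rho, so:

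- ANCOVA = T - rho × e
- pre-post change = T - e
- follow-up comparison without the covariate = T, whatever e is

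For T = 0.5 and rho = 0.5 (for example, at e = 0.25: 0.5 - 0.5 × 0.25 = 0.375 and 0.5 - 0.25 = 0.25):

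| e | -0.5 | -0.25 | 0 | 0.25 | 0.5 |
|---|---|---|---|---|---|
| ANCOVA | 0.75 | 0.63 | 0.50 | 0.38 | 0.25 |
| Pre-post change | 1.00 | 0.75 | 0.50 | 0.25 | 0.00 |

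**Rejection when T = 0** (a practice effect that has gone by week 4), rho = 0.5. The ANCOVA was simulated with the interaction term in the model. With two time points, the four-group by time test is the one-way F test on the change score, with 3 and 36 df and noncentrality 40 × (e/2)² / (2(1 - rho)). At e = 0.25 this is 40 × 0.015625 / 1 = 0.625.

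| size of e | 0 | 0.1 | 0.25 | 0.5 |
|---|---|---|---|---|
| Spurious ANCOVA effect (sign opposite to e) | 0 | 0.05 | 0.13 | 0.25 |
| ANCOVA game effect rejects | 5.0% | 5.4% | 7.2% | 13.6% |
| Noncentrality, group by time | 0 | 0.1 | 0.625 | 2.5 |
| Group by time rejects | 5% | 5.5% | 8.5% | 21.2% |
| Follow-up without covariate rejects | 5% | 5% | 5% | 5% |

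If praise and game each shift the first score by e, the noncentrality doubles and the group by time test rejects about 6%, 12% and 40% at e = 0.1, 0.25 and 0.5. At e = 0.25 with rho = 0.3 and 0.7, the ANCOVA rejects about 6% and 11%, and the group by time test about 7.5% and 11%.

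**Power of the game effect, T = 0.8, rho = 0.5**

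| e | 0 | 0.1 | 0.2 | 0.25 | 0.5 |
|---|---|---|---|---|---|
| ANCOVA with first IMI as covariate | 80% | 75% | 68% | 65% | 46% |
| Follow-up without covariate | 69% | 69% | 69% | 69% | 69% |

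The two are level near e = 0.2 here. The crossover moves to about e = 0.1 at rho = 0.3 and about e = 0.3 at rho = 0.7.

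**The case against.** The strongest reply is that there are two practices. The IMI entry speaks of the child practising with the research assistant. The training section speaks of the family practising while staff observe. A short, plain try-out for the child before disclosure would satisfy every section, and giving a task-evaluation questionnaire after some experience of the task is sensible and deliberate. This reading is possible, so exposure of the covariate is not established. But no section describes such a try-out, and the design section gives each child a link that already carries the assigned features. The reply therefore shows which sentence is missing; it does not show that none is needed.

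The second reply is about size. The larger error rates need a half-SD shift from one short session, and nothing in the documents supports that. At e = 0.1 the planned tests stay at roughly 5% to 6%. The pre-post rates count as errors only if the target is the total effect at follow-up. The IMI is a secondary, exploratory measure in a 40-family proof-of-concept trial. All of this stands. It limits the weight of the point without removing the conflict.

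**Conclusion.** The concern holds. The stated orders cannot all apply to the one practice session described. If the baseline IMI follows that session, both planned IMI analyses rest on a post-exposure score. That second part is conditional, because the documents leave a separate neutral practice open.

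The bias is -rho × e in the ANCOVA and -e in the pre-post contrast. Its sign and size are unknown: negligible at e = 0.1 SD, material from about 0.25 SD. The illustrations rest on assumed T, e and rho, normal scores with equal SDs and a 5% level. The conflict in the text rests on none of these. It should be fixed, with confidence medium and reach limited to the secondary IMI analyses.

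**What to change.** State one order in Study Flow, Family dDSM Training and the IMI entry:

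1. every child practises on a common feature-free log;
2. baseline IMI;
3. disclosure of condition;
4. feature-specific training on the personal log.

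This keeps the familiarity aim and makes the IMI a valid covariate. If it is already what happens, one sentence saying so closes the point.

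For any family assessed after featured practice, record the order and label the first IMI as post-exposure. Report the follow-up comparison without that covariate beside the planned ANCOVA, and do not read between-arm pre-post change as the total effect. Say in advance how a disagreement will be read: the comparison without the covariate is the one whose estimate of the total effect does not depend on e.

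**Cost.** A few minutes per visit, one neutral practice link (re-ordering alone is not enough, since the personal link carries the features) and a few sentences of text. Children in the game and praise arms would meet the plain log first, so a small contrast effect is possible. A change made mid-trial leaves two kinds of first IMI. Leaving out a clean covariate costs power: at T = 0.8, 69% against 72%, 80% and 92% for rho = 0.3, 0.5 and 0.7. As e is unknown, both analyses should be shown rather than one replaced.
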